5.1.6 Physical Examination and Vital Signs

Physical examination findings will be summarized by visit in the ITT population using percentages. An additional table will summarize absolute and relative changes from baseline to each follow up visit in physical examination and vital signs.

5.1.7 Local Laboratory Tests

For the ITT Population, local laboratory blood test results of red blood cells (RBC), white blood cells(WBC), hemoglobin, platelet count, serum carbohydrate antigen CA-19-9, serum creatinine, total bilirubin, alanine aminotransferase (ALT) and aspartate aminotransferase(AST) will be categorized as normal (N), out of normal ranges but not clinically significant (OR), and out of range and clinically significant (CS) at baseline, CA-19-9 will be summarized at Week 2-6 following completion of RT too.

5.2 Interim Analyses

There is no interim analysis planned for the study.

5.3 Subgroup Analyses

Data may be presented separately for localized (resectable, BRPC and LAPC) subjects as well as resected and unresected subjects, when appropriate.

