Week 2-6 Following Completion of RT (Restaging & Evaluation for Potential Resection at time of CT)	
 Physical Examination: including sitting blood pressure, pulse, temperature, weight, anticoagulation status, Zubrod Performance Score CT for restaging (also will evaluate TraceIT Persistence) Assessment of duodenal focused Adverse Events documented using NCI CTCAE Other Adverse Events per NCI CTCAE Changes in concomitant medications used to treat intestinal symptoms CA-19-9 level Pancreaticoduodenectomy should be targeted to be performed within 8 weeks after the completion of RT if applicable. 
Restaging and determination of resectability will be performed in accordance with the standard institutional practices.

Resected Subjects (At time of resection)	
 Physical Examination: including sitting blood pressure, pulse, temperature, weight, anticoagulation status, Zubrod Performance Score Assessment of duodenal focused Adverse Events documented using NCI CTCAE if available Other Adverse Events per NCI CTCAE if available Changes in concomitant medications used to treat intestinal symptoms

Resected Subjects (Histopathology record)	
 Incidence of complete or partial response (Path PR and Path CR) Pathologic duodenal damage score rated by a local board-certified gastrointestinal surgical pathologist using the methods outlined by Verma et al.,¹ where: 
 1=no/minimal signs of mucosal damage: villi remain long and slender, epithelial cells have abundant eosinophilic cytoplasm with few mitotic figures, and the lamina propria have normal amounts of inflammatory cells including few or no neutrophils. 2=moderate damage where villi are blunted or absent, epithelial cells have reactive/reparative changes with basophilic cytoplasm, increase mitotic figures, and/or small erosions or focal ulcerations; the lamina propria show increased inflammation including eosinophils and neutrophils. 3=severe damage with diffuse epithelial damage absent with or without extensive ulcerations and residual surviving epithelium displaying marked reactive/reparative changes; lamina propria replaced with granulation tissue and/or overlying fibrinoid inflammatory exudates with numerous neutrophils or marked damage.

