6.4.4 Screening/Baseline Assessments (within 45 days prior to planned TraceIT hydrogel injection)

Subjects who appear to meet the eligibility criteria will be consented for the study and will undergo screening. Information to be collected at this visit includes:

- Demographic information: date of birth, weight and height, race
- Disease documentation: tumor location, initial resectability status, tumor staging, largest pre-treatment dimension of tumor (cm)
- Medical/Surgical History/Current status: concomitant medical conditions, prior medical conditions, prior surgeries, prior therapies (e.g., induction chemotherapy)
- Physical Examination: including sitting blood pressure, pulse, temperature, weight, anticoagulation status, Zubrod Performance Score
- Laboratory testing for hematology plus platelets, creatinine, AST/ALT and bilirubin and baseline serum carbohydrate antigen (CA) 19-9
- Pregnancy test for women of child-bearing potential

- EORTC-QLQ-C30 and QLQ-PAN26
- Assessment of baseline duodenal symptoms per NCI CTCAE
- Baseline concomitant medications

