7.4 Subgroup Analyses

Data may be presented separately for localized (resectable, BRPC and LAPC) subjects as well as resected and unresected subjects. Details will be provided in the statistical analysis plan.

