3.3 Exploratory Effectiveness Endpoint

The exploratory effectiveness endpoints are defined as:

- Incidence of resection
- Histology of duodenal tissues when resection is performed
- Incidence of acute (within 3 months) and late (>3 months) duodenal toxicity (for unresected subjects)
- Theoretical dose escalation from post-TraceIT treatment plan
- TraceIT persistence (at 6-months post-TraceIT in nonresected subjects)
- Change from baseline in EORTC QoL (QLQ-C30) and QLQ-PAN26
- Comparability of visualization of the fiducial marker and TraceIT hydrogel using a standardized visualization score
- Progression free and overall survival through follow-up

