3.3.1 Statistical Methods

The proportion of resected subjects in the MITT or PP population, localized (resectable, BRPC or LAPC) subgroup may be calculated with an exact (Clopper-Pearson) 95% confidence interval for the true proportion, when appropriate.

The incidence of acute (within 3 months) and late (>3 months) duodenal toxicity for unresected subjects will be reported by CTCAE grade and timing.

Histology of duodenal tissue (Duodenum Damage Score) will be summarized for those subjects when resection is performed.

The summary of theoretical dose escalation from post-TraceIT treatment plan, and , migration and stability at 2-6 weeks post-TraceIT, TraceIT persistence at 6-months post-TraceIT in non-resected subjects will be presented in separated table. The pre-TraceIT and post-TraceIT duodenal space measured by site during index procedure and/or by independent assessors will be summarized separately. Average duodenal space will be

calculated if the measurements were taken from multiple observation points or duplication.

The EORTC QLQ-C30 is a questionnaire developed to assess the quality of life of cancer patients. The pancreatic cancer module QLQ-PAN26 is intended for patients at all disease stages undergoing surgical resection, palliative surgical intervention, endoscopic palliation or palliative chemotherapy. Changes in Quality of Life Measures as assessed overall and subdomains (scales) of the EORTC-QLQ-C30 and QLQ-PAN26 will be evaluated.

The five functional scales (physical, role, emotional, cognitive and social), three symptom scales (fatigue, nausea & vomiting and pain), a global health status/QOL scale, and six single items (dyspnea, insomnia, appetite loss, constipation, diarrhea and financial difficulties) from EORTC-QLQ-C30 will be summarized according EORTC QLQ-C30 Scoring Manual third edition.

The fifteen symptom items and two functional scales from QLQ-PAN26 will be analyzed according EORTC QLQ-PAN26 Scoring Manual 2.2.

Those analysis will be repeated by localized (resectable, BRPC and LAPC), as well as resected and unresected subgroup, if applicable. Scores will be compared to baseline using either a paired t-test or Wilcoxon Signed-Rank test when appropriate.

The result of comparability of visualization of the fiducial marker and TraceIT hydrogel will be summarized using a standardized visualization score for all subjects injected with TraceIT Tissue Spacer.

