5.1.2 Demographics and Baseline Characteristics

Subjects will be summarized with respect to baseline demographics and clinical characteristics (e.g., age, sex, tumor grade, resection status etc.) by ITT, MITT and PP population. These will be summarized by descriptive statistics including means, medians,

standard deviations and ranges (for quantitative variables) and percentages (for categorical variables).

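### Resection happens after radiotherapy and is itself an endpoint, yet the SAP lists it as a baseline characteristic and groups results by it without saying when group membership is fixed

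*SAP*

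**What the plan says.** **When resection occurs.** Protocol 6.3.2 excludes anyone with a previous resection of the tumour, so every subject enters unresected. The Protocol Summary places restaging, which decides on surgery, 2-6 weeks after therapy. It adds: "Pancreaticoduodenectomy should be targeted to be performed within 8 weeks after the completion of RT if applicable". SAP 3.3 lists "Incidence of resection" as an exploratory endpoint.

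**Baseline.** SAP 5.1.2 summarises "clinical characteristics (e.g., age, sex, tumor grade, resection status etc" and so on. Protocol 7.6.1 has the corresponding list without that item. What Protocol 6.4.4 collects at screening is "initial resectability status".

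**Subgroups.** Protocol 7.4 allows separate presentation by resection and promises: "Details will be provided in the statistical analysis plan". SAP 5.3 largely repeats the protocol sentence: "Data may be presented separately for localized (resectable, BRPC and LAPC) subjects as well as resected and unresected subjects, when appropriate". It does not say which endpoints are split, when membership is fixed, or how time before surgery is treated. SAP 3.3.1 is firmer for quality of life: those analyses will be repeated by resectability class, "as well as resected and unresected subgroup, if applicable". The only test there is of each score against the subject's own baseline.

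**Survival.** SAP 3.3.1 measures PFS and OS from the start of induction chemotherapy. It does not mention resection in either definition.

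**The concern.** Resection is something that happens to a subject during the study. Used as a baseline descriptor, it presents an outcome as a pre-treatment feature. Used as a grouping factor for data recorded before surgery, it sorts subjects by a future event. Those who go on to surgery are likely to be those who stayed well and did not progress, so a difference between the groups before surgery may reflect who was selected and nothing else.

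For time-to-event outcomes there is a further mechanical problem. A resected subject must have lived until surgery, and every earlier death falls in the unresected group. A reader of such a display could credit surgery, or the spacer, with an advantage created by the grouping. The SAP carries no caution against this.

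**Working it through.** The plan gives no figure to reproduce here, so the check is one of timing, followed by an illustration on stated assumptions.

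**1. Timing of surgery.** From the protocol: RT starts no later than 28 days after the index procedure (6.4.9), and surgery is targeted within 8 weeks (56 days) after RT (6.4.11). RT duration is assumed to be 1, 2 or 6 weeks. At the outer limits, index to surgery is:

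- 1 week: 28 + 7 + 56 = 91 days (3.0 months)
- 2 weeks: 28 + 14 + 56 = 98 days (3.2 months)
- 6 weeks: 28 + 42 + 56 = 126 days (4.1 months)

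**2. Quality-of-life visits against that window.** Scores are collected at baseline, the final RT fraction, and Months 3, 6, 12 and 18 after the index procedure (Protocol 6.4.1, Table 2). None are collected at the Week 2-6 restaging visit. With a month of 30.44 days:

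- Baseline and final fraction: always before the decision on surgery.
- Month 3 (±14 days): days 77 to 105, so before or after surgery depending on the subject.
- Month 6 (earliest): 182.6 − 14 = day 168, later than day 126, so after any on-target surgery.

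**3. PFS or OS, if split.** The interval from induction to enrolment must be survived by both groups and cancels. Only the window *W* from enrolment to surgery differs. Assume exponential event times after enrolment with median *m*, no effect of resection, and a random fraction *p* of subjects resected if event-free at *W*. With S(W) = 2^(−W/m):

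- resected median = W + m
- unresected median *t* solves S(t) = (1 − p·S(W)) / (2(1 − p)), provided t > W

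For PFS with m = 9, W = 3, p = 0.5:

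- S(3) = 0.794, so 21% fail before surgery and all of them count as unresected.
- Resected median: 3 + 9 = 12.0 months.
- Unresected: S(t) = 1 − 0.5 × 0.794 = 0.603, so t = 6.6 months.
- Artificial gap: 5.4 months.

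For OS, over assumed medians of 6 to 24 months, W of 3.0 or 4.1 and p of 0.3 or 0.5, the smallest and largest gaps are:

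- m = 6, W = 3, p = 0.3: S(t) = (1 − 0.3 × 0.707)/1.4 = 0.563, t = 4.98, gap 9 − 4.98 = 4.0 months.
- m = 24, W = 4.1, p = 0.5: S(t) = 1 − 0.5 × 0.888 = 0.556, t = 20.33, gap 28.1 − 20.33 = 7.8 months.

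Simulation of the same scenarios agrees to within 0.1 month. Comparing only subjects alive at *W*, by their status then, brings the gap to about zero.

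**4. Where a landmark must sit.** At restaging, surgery is still ahead by 8 − 6 = 2 to 8 − 2 = 6 weeks at the outer limit. With m = 9 and p = 0.5, counting from restaging and grouping by eventual resection leaves 9.5 against 8.6 months for a 2-week delay (gap 0.9) and 10.4 against 7.8 for a 6-week delay (gap 2.6). The landmark therefore belongs at the end of the surgery window.

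**5. Group sizes.** With six subjects, the chance that one group holds none or one is 22% at a resection rate of 50%, and 43% at 30% or 70% (binomial). With three subjects in a group, the smallest two-sided signed-rank p-value is 2/2³ = 0.25.

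**The case against.** A reader might infer that the SAP plans a biased PFS and OS comparison by resection. It does not. The sentence in SAP 3.3.1 about repeating analyses by subgroup follows the questionnaire paragraphs and precedes the survival definitions. For survival there is only the permissive clause in 5.3, which leaves the analyst free not to split.

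A reader might also extend immortal time to quality of life. That is a time-to-event problem and does not describe change scores. No test between resected and unresected subjects is planned, and nothing in the documents shows that the split would favour resected subjects; major surgery could lower their scores. Nor does the induction start date create the bias, since all enrolled subjects survived to enrolment.

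The term *resection status* is probably loose wording for resectability, because resection would be constant at baseline. Separate presentation is also legitimate where an item exists in one group only: the Month 6 MRI (unresected), duodenal histology and post-surgical complications (resected).

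Finally, the study has six subjects, no formal hypotheses and no significance level, and no decision depends on the split.

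All of this stands, and it limits the point. It does not supply the missing rule on when membership is fixed, and on either reading the baseline label needs the same edit.

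**Conclusion.** The point holds as a minor one. Two things are established from the documents alone: SAP 5.1.2 names as a baseline characteristic something that can only occur later, and SAP 3.3.1 groups quality of life by resection with no limit on visits, although the final-fraction scores always precede the surgery decision and Month 3 scores may precede surgery. For quality of life the defect is selection on a later event, and its size cannot be computed from the documents.

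For PFS and OS the bias is conditional on using the split that 5.3 permits. The gap of roughly 4 to 8 months rests on assumed medians, resection fractions, RT durations, exponential times and random selection for surgery. It shows direction and order of magnitude in a large sample. It is not a forecast for six subjects, and the longer assumed medians would not be reached within 18 months of follow-up.

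**What to change.** 1. **SAP 5.1.2:** replace *resection status* with *initial resectability status*.
2. **SAP 3.3.1 and 5.3, quality of life:** show scores collected before surgery for all subjects together. Split by resection only at visits after the surgery decision is complete, and classify each subject by actual status at that visit. On the timing above, this pools baseline, the final fraction and Month 3, and allows the split from Month 6.
3. **PFS and OS, if shown by resection:** set a landmark at the end of the surgery window, for example 8 weeks after RT, the protocol's own target. Include subjects alive and progression-free then, grouped by status at that date; anyone resected later stays in the unresected group. Alternatively, show individual timelines marking the surgery date, which suits six subjects better.
4. **Labelling:** call all such displays descriptive, and say that a landmark removes immortal time but not the selection of fitter patients for surgery.

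Items that exist only in resected or only in unresected subjects stay as planned. The cost is a few lines of SAP text and the loss of a descriptive split of pre-surgery data.

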5.4 Justification of Pooling

The study will be conducted at up to 4 investigational sites in the United States for six subjects. Poolability will not be tested for this feasibility study due to small sample size.

5.5 Multivariable Analyses

No multivariable analyses is planned for this six subject feasibility study.

5.6 Changes to Planned Analyses

Any changes to the planned statistical analyses made prior to performing the analyses will be documented in an amended Statistical Analysis Plan approved prior to performing the analyses. Changes from the planned statistical methods after performing the analyses will be documented in the clinical study report along with a reason for the deviation.

6 VALIDATION

All clinical data reports generated per this plan will be validated per [90702587](#), Global WI: Clinical Data Reporting Validation.

7 PROGRAMMING CONSIDERATIONS

7.1 Statistical Software

All statistical analyses and data manipulation will be performed using SAS 9.4 or higher for Windows or other validated statistical software.

7.2 Format of Output

SAS output delivery system supported RTF formats will be used. However, tables will be sent to clinical in a WORD or PDF format.

7.3 Rules and Definitions for calculated variables

Rules for programming will be documented accordingly in the SAS code or in the specific table or listing footnotes. This may include references to CRF pages, manipulation of variables, or other appropriate identifiers.
